11.3.2. BRIEF PAIN INVENTORY FOR DIABETIC PERIPHERAL NEPHROPATHY (BPI-DPN)

The pain severity and pain interference will be calculated for each subject at each required visit based on the BPI-DPN instruction. The pain severity, pain interference and their change from baseline (post-treatment – baseline) will be summarized by study visit and treatment arm using the method for continuous variables.

11.3.3. MICHIGAN NEUROPATHY SCREENING INSTRUMENT (MNSI)

Total score of patient history and of physical assessment will be calculated for each subject at each required visit. The total score of the history, the total score of the physical assessment, and their change from baseline (post-treatment – baseline) will be summarized by study visit and treatment arm using the method for continuous variables.

11.3.4. PATIENTS' GLOBAL IMPRESSION OF CHANGE (PGIC)

Subjects will be asked to assess the level of the change of their overall status since the start of the study (scale of 1 to 7) at Day-30, Day-60, Day-90, 6-Month, and 9-Month Visits. PGIC score will be summarized by study visit and treatment arm using the method for continuous variables.

11.3.5. PAIN INTERFERENCE WITH SLEEP

Subjects will be asked to rate the score of pain interfering with sleep in the 7-Day Daily Pain and Sleep Interference Diary. The average of the pain-interference score will be calculated for each subject at each required visit. The average pain-interference score and the change from baseline (post-treatment – baseline) will be summarized by study visit and treatment arm using the method for continuous variables.

11.3.6. Brief Peripheral Neuropathy Screening (BPNS)

Total score of the BPNS will be summarized at the Screening and 6-Month visits using the method for continuous variables. The change from the Screening to the 6-Month visit (6-Month – Screening) will also be summarized.

11.4. Multiplicity Adjustments

There will be no adjustments for multiple comparisons or interim analyses.

12. SAFETY ANALYSES

All subjects who received one or more study injections will be included in the safety analyses, analyzed according to the study treatment actually received.

12.1. Study Drug Exposure

Study drug exposure (number of injections and total volume administered) will be summarized by treatment arm for Day 0 and Day 14 using descriptive statistics for continuous variables.

12.2. Injection Site Reaction

Assessments of injection site reaction (None and Grade 1, 2, and 3), ulceration (None and Grade 2 to 5), and allergic reaction (None and Grade 1 to 5) are planned for Day 0 (post-dose) and Day 14 (pre- and post-dose). The number and percentage of subjects with an injection site reaction will be summarized descriptively by treatment arm and study visit.

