The number of copies of VM202 in whole blood will be determined at Day 0 (pre-injection, and 2 hours [\pm 1 hour] post injection), at Day 14 (pre-injection, and 2 hours [\pm 1 hour] post injection), Day 21, Day 30, Day 60 and Day 90.

Serum chemistry and hematology will be determined on Day 0, Day 30, Day 90 and 9 months. HbA1c will be determined on Day 90, 6 months and 9 months.

VAS and Brief Pain Inventory for Diabetic Peripheral Neuropathy (BPI-DPN) will be recorded at Day 0, Day 30, Day 60, Day 90, at 6 months and 9 months. Patients' Global Impression of Change (PGIC) will be recorded at Day 30, Day 60, Day 90, at 6 months and 9 months. MNSI will be conducted at 6 months and 9 months to track disease progression. Skin biopsy will be repeated at 6 months and the symptoms portion of the Brief Peripheral Neuropathy Screening (BPNS) will be recorded at 6 months.

The Daily Pain and Sleep Interference Diary will be filled out by patients prior to the Day 90, and the 6 Month and 9 Month visits.

Retinal fundoscopy will be conducted at 9 months. Adverse events, concomitant medications and vital signs will be recorded throughout the 9 month follow-up period, while injection site reactions will be assessed starting on Day 0 through Day 60.

A summary of the schedule of evaluations and visits from screening through the end of the study can be found in [Appendix 1](#).

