3.4.10. DAY 21 \pm 3 DAYS

- Concomitant Medications
- Vital Signs
- Copies of VM202 in whole blood
- Injection site assessment
- Adverse event assessment

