4.2.13. INJECTION SITE REACTION ASSESSMENT

Local injection sites reactions will be assessed on Day 0 post injection, Day 14 pre and post injection, Day 21, Day 30 and Day 60 by the National Cancer Institute's Common Terminology for Adverse Events v3.0. The grading categories are as follows and will be recorded on the CRF as described in Table 3.

Table 3. Injection Reaction Assessment

ADVERSE EVENT	GRADE 1	GRADE 2	GRADE 3	GRADE 4	GRADE 5
Injection site reaction	Pain, itching, erythema	Pain or swelling, with inflammation or phlebitis	Ulceration or necrosis that is severe; operative intervention indicated		
Ulceration		Superficial ulceration < 2 cm size; local wound care; medical intervention indicated	Ulceration ≥2 cm size; operative debridement, primary closure or other invasive intervention indicated (e.g. hyperbaric oxygen)	Life-threatening consequences; major invasive intervention indicated (e.g., complete resection, tissue reconstruction, flap, or grafting)	Death
Allergic reaction / hypersensitivity	Transient flushing or rash; drug fever < 38°C (<100.4°F)	Rash; flushing; urticaria; dyspnea; drug fever ≥38°C (≥100.4°F)	Symptomatic bronchospasm, with or without urticaria; parenteral medications(s) indicated; allergy-related edema/ angioedema; hypotension	Anaphylaxis	Death

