Serum HGF		✓		✓			✓	✓	✓			✓ ¹
Copies of VM202 in whole blood		✓	✓***	✓	✓***	✓	✓	✓	✓			✓ ¹
Skin biopsy		✓								✓		
Treatment												
Injection site reaction assessment			✓	✓	✓	✓	✓	✓	✓			✓ ²
Adverse Events			✓	✓	✓	✓	✓	✓	✓	✓	✓	✓

[†] Cancer screening: chest X-ray or chest CT scan if subject has a previous history of tobacco use within 3 months; pap smear and mammogram within past 12 months (females only); PSA within past 3 month (males only); for subjects ≥ 50 years old, colonoscopy within past 10 years; for subjects with a first degree relative with colon cancer, colonoscopy within past 12 months.

^{††} MNSI - Michigan Neuropathy Screening Instrument

1. If withdrawal occurred before Day 90 Visit

2. If withdrawal occurred before Day 60 Visit

* PGIC - Patient's Global Impression of Change

** BPI-DPN - Brief Pain Inventory, diabetic neuropathy specific test

*** 2 hours after injection (± 1 hour)

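### SAP 12.2 names only three of the six scheduled injection-site assessments, so the graded by-visit summary may leave out Days 21, 30 and 60

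*SAP*

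**What the plan says.** SAP 12.2 names three graded outcomes (injection-site reaction, ulceration, allergic reaction) and says that their assessments "are planned for Day 0 (post-dose) and Day 14 (pre- and post-dose". Its next sentence says that the number and percentage of subjects with an injection-site reaction "will be summarized descriptively by treatment arm and study visit". The corresponding output, Table 12 in SAP Appendix A, names no visits in its title.

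Protocol 4.2.13 gives a longer list: "Day 0 post injection, Day 14 pre and post injection, Day 21, Day 30 and Day 60". Protocol 3.2 says the same in summary form: "injection site reactions will be assessed starting on Day 0 through Day 60". The protocol's visit lists for Days 21, 30 and 60 (3.4.10 to 3.4.12) each carry the item "Injection site assessment".

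The SAP's own schedule (Section 3, Table 2) has a row for "Injection site reaction assessment" that is ticked at Days 21, 30 and 60 as well. It also has an early-withdrawal tick with the footnote "If withdrawal occurred before Day 60 Visit".

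**The concern.** The analysis text of the SAP describes a shorter assessment schedule than the one the trial runs. The three visits it does not name all fall after the last injections, and they are the only scheduled graded looks at delayed local reactions to the second round.

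Safety is the primary objective in SAP 2.1. Each subject receives 64 injections per round, and the only toxicity that Protocol 1.5 reports from the non-clinical programme is mild, transient injection-site irritation. A summary of local reactions that stopped on the day of the second round would be a thin account of a central safety outcome. Because Table 12 names no visits, SAP 12.2 is the only place in the analysis text that tells a programmer which visits to tabulate.

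**Working it through.** No power, error-rate or event-count calculation applies. The check is a comparison of schedules.

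| Time point | Protocol 4.2.13 | Protocol visit lists (3.4.8 to 3.4.13) | SAP Table 2 | SAP 12.2 |
|---|---|---|---|---|
| Day 0 post-dose | yes | yes | yes | yes |
| Day 14 pre-dose | yes | yes | yes | yes |
| Day 14 post-dose | yes | yes | yes | yes |
| Day 21 | yes | yes | yes | not named |
| Day 30 | yes | yes | yes | not named |
| Day 60 | yes | yes | yes | not named |
| Day 90 | no | no | ticked, as the table was read | not named |

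1. **Count.** The protocol schedules 6 time points and SAP 12.2 names 3. Not named: 6 − 3 = 3.

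2. **Position relative to dosing.** Injections are given on Days 0 and 14. The unnamed visits fall nominally 21 − 14 = 7, 30 − 14 = 16 and 60 − 14 = 46 days after the second round.

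3. **What each round keeps under the literal reading.** For the first round, Day 0 post-dose is a same-day look and Day 14 pre-dose is a delayed look. For the second round, only Day 14 post-dose remains, which is a same-day look, and 0 of the 3 later scheduled assessments are named. The second round is 2 calves × 32 = 64 of the 2 × 2 × 32 = 128 injections per subject.

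4. **Early withdrawal.** Protocol 3.5.2 and Appendix 1, and SAP Table 2, provide an injection-site assessment for subjects who leave before Day 60. SAP 12.2 does not mention it.

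5. **The other route to the report.** Protocol 5.2 requires adverse events of any severity to be recorded from first dosing to the 9-month visit. SAP 12.3 summarises treatment-emergent events by preferred term, maximum severity and relationship, with no visit cut-off. A delayed reaction entered as an adverse event would therefore be tabulated. Three features keep these tables from replacing the graded summary:
   - intensity under Protocol 5.2.2 is mild, moderate or severe, whereas local reactions are graded by the criteria in Protocol Table 3;
   - the tables are not by visit;
   - SAP 12.3 classifies relationship to study drug only, although Protocol 6.3.3 also calls for relationship to the injection procedure.

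   Protocol 4.2.13 does not say that every graded finding must also be entered as an adverse event.

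6. **Outcomes covered.** SAP 12.2 introduces three graded outcomes, but its summary sentence names only injection-site reaction. It is not explicit that ulceration and allergic reaction will be tabulated.

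**The case against.** The strongest case on the other side is that nothing is actually excluded. The sentence naming the three time points describes when assessments are planned and does not say that the analysis stops there. The summary sentence refers only to study visit. SAP Table 2 shows the later visits, and SAP 5.1 says that data at each scheduled follow-up visit are analysed under the nominal visit. A programmer working from the whole SAP could reasonably tabulate all six time points.

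This stands in part. It shows that the SAP is internally inconsistent, not that exclusion is settled. It does not remove the defect, because the summary sentence directly follows the three-visit list and nothing else in the analysis text names the visits. Two programmers could build different tables from the same plan.

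A reader might go further and infer that no delayed reaction after the second round would be analysed at all, and that local tolerability would look better than the data show. The documents do not support that. A new ulcer or area of necrosis after Day 14 meets the adverse-event definition in Protocol 5.1. Adverse-event assessment is listed at Days 21, 30 and 60 beside the injection-site check, and SAP 12.3 would carry the event into its tables. A flattering picture would need both the restrictive reading of SAP 12.2 and a finding that was not also reported as an adverse event.

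A reader might also want a probability that such a case occurs. The documents give no rate of delayed local reactions, and any figure from an assumed rate would ignore capture through the adverse-event tables.

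**Conclusion.** The schedule stated in SAP 12.2 is wrong against Protocol 4.2.13, Protocol 3.2, the protocol's visit lists and SAP Table 2. It names 3 of 6 graded time points. The 3 left out are all of those after the day of the second injection round.

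The mismatch itself is certain from the text. Its consequence is conditional: if the section is programmed literally, Table 12 loses every delayed graded look at the second round, and such reactions appear only if they are also reported as adverse events, without visit and without the Protocol Table 3 grade. If it is programmed from SAP Table 2, nothing is lost. This is a consistency correction that should be made, on an outcome that falls under the primary objective. It is not evidence that the safety analysis as a whole misses delayed reactions.

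The apparent Day 90 tick in SAP Table 2 carries little weight. The Day 90 visit list (Protocol 3.4.13) and Protocol Appendix 1 show no injection-site assessment there, the footnote to SAP Table 2 uses Day 60 as its limit, and ticks can shift when a table is read from PDF. It is a point to check and not a finding.

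**What to change.** Rewrite SAP 12.2, and the specification of Table 12, so that injection-site reaction, ulceration and allergic reaction are each summarised by grade and arm at Day 0 post-dose, Day 14 pre-dose, Day 14 post-dose, Day 21, Day 30 and Day 60, and at early withdrawal when it occurs before Day 60. Preferably add the worst grade per subject over all these assessments, by arm. That is a useful addition rather than something the protocol promises, since Protocol 6.3.3 asks only for descriptive statistics.

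Check the SAP Table 2 row against the source file and, if the Day 90 tick is really there, reconcile it with the protocol's Day 60 limit.

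The cost is a wording change and a few more table rows. The data are already collected under the protocol, and the change is best made before the randomization codes are unmasked.

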12.3. Adverse Events

All adverse event summaries will be restricted to Treatment Emergent Adverse Events (TEAE), which are defined as those AEs that occurred after dosing and those existing AEs that worsened during the study. Verbatim terms on case report forms will be mapped to preferred terms. It should be noted that only the AEs after the first round of injection will be collected during the study.

The adverse event summaries will be displayed by treatment arm. The number of subjects experiencing a particular event, the percentage of subjects experiencing the event, and the total number of events will be presented. The following summaries will be created:

- TEAE by preferred term;
- TEAE by preferred term and maximum severity. At each level of subject summarization, a subject is classified according to the highest severity if the subject

reported one or more events. AEs with missing severity will be considered severe for this summary;

- TEAE by preferred term and closest relationship to study drug (Related/Not Related). At each level of subject summarization, a subject is classified according to the closest relationship if the subject reported one or more events. AEs with a missing relationship will be considered related for this summary; events classified as ‘possibly’, ‘probably’ or ‘definitely’ will be considered ‘related’.
- Serious TEAEs by preferred term.

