SCHEDULE OF EXAMINATIONS	Screening (Day -60 to Day 0) Day 0 Day 14 ± 1 days Day 21 ± 3 days Day 30 ± 3 days Day 60 ± 3 days Day 90 ± 7 days Month 6 ± 1 month Month 9 ± 1 month
STUDY ENDPOINTS	The primary study endpoint is the change in the average 24 hour pain score (change from baseline to the 6-month follow-up). The difference in the mean of the change in the average 24-hour pain score will be compared between the treatment groups and the placebo arm to determine the treatment effect. The average pain scores will be obtained from the Daily Pain and Sleep Interference Diary (recorded daily by the patient for 7 days during Screening prior to the first round of injections and again, before the 6 month follow-up).
SAFETY	Any subject who receives study drug (VM202 or placebo) will be included in the safety analysis population. Adverse events (including serious adverse events, and adverse events leading to treatment discontinuation) throughout the 9 months follow-up will be described according to severity and to their relationship with the study drug and injection procedure. Descriptive statistics (N, mean, median, SD, minimum and maximum values, where applicable) will be used to characterize safety parameters.
	All subjects will undergo testing as presented in the American Cancer Society Cancer Screening Guidelines as part of their baseline testing to rule out cancer.
PHARMACOKINETICS	Determination of HGF serum levels will be determined immediately pre-treatment on Day 0, immediately pre-treatment on Day 14, on Day 30, Day 60, and Day 90. The number of copies of VM202 in whole blood will be determined at Day 0 (pre-injection, and 2 hours [± 1 hour] post injection), at Day 14 (pre-injection, and 2 hours [± 1 hour] post injection), Day 21, Day 30, Day 60 and Day 90.
OTHER EFFICACY MEASURES	The 24 hour average pain score obtained from the Daily Pain and Sleep Interference Diary will be compared at all other study visits,

as will the Brief Pain Inventory for Diabetic Peripheral Neuropathy (BPI-DPN), the VAS score obtained during follow-up visits, symptoms of the Brief Peripheral Neuropathy Screening (BPNS), the Patients' Global Impression of Change (PGIC), MNSI, and histological findings on skin biopsy.

TABLE OF CONTENTS

INVESTIGATOR'S AGREEMENT.....	2
STUDY SYNOPSIS	3
TABLE OF CONTENTS	10
ABBREVIATIONS	14
PERSONNEL AND FACILITIES.....	15
1. BACKGROUND.....	16
1.1. Diabetes	16
1.1.1. Diabetic Peripheral Neuropathy	16

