5.2. ASSESSMENT OF AEs

All AEs, regardless of severity, occurring following the first study drug administration and the 9 month follow-up visit of the study by a subject must be recorded on the AE form provided with the CRF. This will include the following information:

- Description of the AE
- Date of onset
- Duration
- Frequency
- Severity
- Seriousness (yes/no)
- Treatment
- Outcome
- Relationship to study medication, injection procedure and/or underlying disease

All AEs and SAEs must be followed until resolution, or the condition stabilizes. The Investigator is responsible to ensure that follow-up includes any supplemental investigations as may be indicated to elucidate as completely as possible the nature and/or causality of the AE or SAE. This may include additional laboratory tests or investigations, histopathological examinations, or consultation with other health care professionals. The Sponsor or its designee may request that the Investigator perform or arrange for the conduct of supplemental measurements and/or evaluations.

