5.2.1. AE CAUSALITY

The study investigator will determine whether an AE is related or unrelated to study medication, the procedure (intramuscular injection) and / or the underlying disease using the following criteria:

Not related: An adverse event that is not related to the use of the test article or administration procedure.

Possibly related: An adverse event that might be due to the use of the test article or administration procedure. An alternative explanation, e.g., concomitant study product(s), concomitant disease(s), is inconclusive. The relationship in time is reasonable; therefore, a causal relationship cannot be excluded.

Probably related: An adverse event that might be due to the use of the test article or administration procedure. The relationship in time is suggestive. An alternative explanation is less likely, e.g., concomitant drug(s), concomitant disease(s).

Definitely related: An AE that is due to the use of the test article or administration procedure. The event cannot be reasonably explained by an alternative explanation – e.g., concomitant drug(s), concomitant disease(s).

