6.3.3. SAFETY

Any patient who receives injections (study drug or placebo) will be included in the safety analysis population. Adverse events (including serious adverse events, and adverse events leading to treatment discontinuation) throughout the 9 month follow-up will be described according to severity and to their relationship with the study drug and injection procedure. Descriptive statistics (N, mean, median, SD, minimum and maximum values, where applicable) will be used to characterize safety parameters.

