APPENDIX A: LIST OF TABLES

Table Number	Table Description
1	Subject Disposition And Accountability
2	Demographic Characteristics (Efficacy Analysis Group/ITT Group/Safety Analysis Group)
3	Abnormal Medical History at Baseline (Safety Analysis Group)
4	Peripheral Vascular Disease Intervention History (Safety Analysis Group)
5.1	Visual Analogue Scale for 24-hour Average Pain from Daily Pain and Sleep Interference Diary (Efficacy Analysis Group)
5.2	Visual Analogue Scale for 24-hour Average Pain from Daily Pain and Sleep Interference Diary (ITT Group)
5.3	Visual Analogue Scale for 24-hour Average Pain from Daily Pain and Sleep Interference Diary (ITT Group with Missing Value Imputation at 6 Months)
6.1	Visual Analogue Scale for Pain (Efficacy Analysis Group)
6.2	Visual Analogue Scale for Pain (ITT Group)
7.1	Brief Pain Inventory for Diabetic Peripheral Neuropathy (BPI-DPN) (Efficacy Analysis Group)
7.2	Brief Pain Inventory for Diabetic Peripheral Neuropathy (BPI-DPN) (ITT Group)
8.1	Michigan Neuropathy Screening Instrument (MNSI) (Efficacy Analysis Group)
8.2	Michigan Neuropathy Screening Instrument (MNSI) (ITT Group)
9.1	Patients' Global Impression of Change (PGIC) (Efficacy Analysis Group)
9.2	Patients' Global Impression of Change (PGIC) (ITT Group)
10.1	24-hour Average Pain Interference with Sleep from Daily Pain and Sleep Interference Diary (Efficacy Analysis Group)
10.2	24-hour Average Pain Interference with Sleep from Daily Pain and Sleep Interference Diary (ITT Group)
11	Study Drug Exposure(Safety Analysis Group)
12	Injection Site Reaction (Safety Analysis Group)
13.1	Adverse Events by Preferred Term (Safety Analysis Group)
13.2	Adverse Events by Maximum Severity (Safety Analysis Group)
13.3	Adverse Events by Relationship to Study Drug (Safety Analysis Group)
13.4	Serious Adverse Events by Preferred Term (Safety Analysis Group)
13.5	Serious Adverse Events by Maximum Severity (Safety Analysis Group)
13.6	Serious Adverse Events by Relationship to Study Drug (Safety Analysis Group)
14.#	Hematology – Test # Shift from Baseline (Safety Analysis Group)
15.#	Chemistry – Test # Shift from Baseline (Safety Analysis Group)
16	HGF Serum Level (Safety Analysis Group)
17.#	Vital Signs – Parameter # (Safety Analysis Group)

18	Retinal Fundoscopy- Shift from Baseline (Safety Analysis Group)
19	Prior and Concomitant Medications (Safety Analysis Group)

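### SAP 12.2 ends injection-site assessments at Day 14 against the protocol's Day 60, and SAP 12.3 neither summarizes AEs by relationship to the injection procedure nor identifies those leading to treatment discontinuation

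*SAP*

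**What the plan says.** **Adverse events.** Protocol 6.3.3 says that adverse events "will be described according to severity and to their relationship with the study drug and injection procedure". The synopsis says the same and, like 6.3.3, names a particular subset: "adverse events leading to treatment discontinuation) throughout the 9 months follow-up will be described according to severity". Protocol 5.2 puts the attribution on the AE form: "Relationship to study medication, injection procedure and/or underlying disease". The causality grades in Protocol 5.2.1 take drug and procedure together; the possible and probable grades both begin "An adverse event that might be due to the use of the test article or administration procedure".

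SAP 12.3 lists four summaries. Its only relationship summary is "TEAE by preferred term and closest relationship to study drug (Related/Not Related"). Appendix A follows suit: Table 13.3 is "Adverse Events by Relationship to Study Drug (Safety Analysis Group") and Table 13.6 is its serious-event counterpart.

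**Injection sites.** SAP 12.2 says that assessments of injection-site reaction, ulceration and allergic reaction "are planned for Day 0 (post-dose) and Day 14 (pre- and post-dose"). Protocol 4.2.13 schedules them on "Day 0 post injection, Day 14 pre and post injection, Day 21, Day 30 and Day 60". Protocol 3.2, the visit lists in 3.4.10 to 3.4.12, and Appendix 1 agree with 4.2.13. SAP Table 2 ticks injection-site visits after Day 14, and its early-withdrawal footnote for that row refers to the Day 60 visit.

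**The concern.** SAP 2.1 makes the safety of intramuscular administration the primary objective. Each subject receives 64 injections per visit at two visits, so harm from the procedure is part of what the trial is meant to describe. The protocol collects the investigator's judgment on that harm and says it will be reported, but the SAP makes no provision for reporting it.

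The injection-site table has a related problem. If a programmer follows the days in SAP 12.2, the last reading is taken on the day of the second round. The visits best placed to show a reaction developing or persisting after that round would be absent from the one table designed for it.

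There is also a risk of misclassification. Because the causality grades name drug and procedure together, and SAP 12.3 does not say which attribution feeds the study-drug tables, an event judged due only to the needle could be counted as drug-related.

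**Working it through.** No power or error-rate figure is involved. The check sets the texts side by side.

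**Injection-site time points**

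| Time point | Protocol 4.2.13 | SAP 12.2 |
|---|---|---|
| Day 0 post | yes | yes |
| Day 14 pre | yes | yes |
| Day 14 post | yes | yes |
| Day 21 | yes | not named |
| Day 30 | yes | not named |
| Day 60 | yes | not named |

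SAP 12.2 names 3 of 6. Injections per subject (Protocol 3.4.8.2 and 3.4.9.2): 32 per calf × 2 calves = 64 per visit, and 64 × 2 visits = 128. The second round is 64 of 128, and SAP 12.2 names no assessment after the day it is given. SAP Table 2 does continue past Day 14, so the SAP disagrees with itself as well as with the protocol.

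**AE outputs**

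| Item in Protocol 6.3.3 | SAP 12.3 (4 summaries) | Tables 13.1–13.6 (6 tables) |
|---|---|---|
| Severity | yes | 13.2, 13.5 |
| Relationship to study drug | yes | 13.3, 13.6 |
| Relationship to injection procedure | 0 of 4 | 0 of 6 |
| Events leading to treatment discontinuation identified | 0 of 4 | 0 of 6 |

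No redaction appears in SAP 12.2, SAP 12.3 or the table list that would account for the gaps.

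**What treatment discontinuation can mean here.** Treatment is two rounds 14 days apart, so in practice it means a missed Day 14 round. Three other parts of the SAP come close:

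- SAP 7 counts subjects who received all planned doses and gives the primary reason for leaving the *study*.
- SAP 12.1 shows Day 14 exposure.
- SAP 11.1.1 has to identify subjects who discontinued early because of AEs, for imputation.

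None of these shows the AE behind a missed second round when the subject stays in follow-up.

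**Can the data support the missing outputs?** Procedure relationship is collected (Protocol 5.2). The AE fields listed there include no link from an event to a missed dose, and the only AE reason in Protocol 3.5.2 is labelled as pre-treatment. Whether the CRF holds that link cannot be settled from the documents.

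**The case against.** The other side has good arguments, and several limit how far the point can go.

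- **The protocol says described, not tabulated.** This stands. A reader might cross the AE sets with the descriptors and count several missing tables. The parenthesis in 6.3.3 only says what the AE set includes; it does not promise a separate table for each combination. On that plain reading, Tables 13.2 and 13.3 already contain the serious and discontinuation events. What remains is one missing descriptor (procedure relationship) and no means of telling which events led to discontinuation.
- **The SAP's lists are not exhaustive.** Also true. SAP 12.3 names one serious-event summary, while Appendix A has three. Appendix A has no table for the 50% responder analysis, the BPNS or VM202 copies, all of which the text plans. SAP 5 also mentions data listings. Absence from a list is therefore not proof of exclusion. But the SAP does not specify the content of an AE listing, so this softens the gap without closing it.
- **Later reactions are not necessarily lost.** A reader might infer that any reaction after Day 14 goes unreported. The documents do not support that. SAP 12.2 goes on to say that reactions are summarized by arm and study visit, with no day limit, and Table 12's title has none. AEs of any severity are recorded to 9 months (Protocol 5.2 and 5.3), so a late reaction reported as an AE would enter Tables 13.1 to 13.3. The protocol still schedules the later assessments whatever the SAP says. The short day list may be a drafting slip, but it is the only statement in SAP 12.2 of which visits are planned, and it is wrong.
- **Procedure harm shows in the placebo arm.** Partly. Every arm has the same number of injections, so the between-arm contrast mainly isolates drug. Placebo AE rates, however, mix procedure effects with background illness in a planned 20 subjects. The investigator's attribution is the direct record.

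**Conclusion.** The point holds in a limited form. SAP 12.2 states an injection-site schedule that contradicts the protocol and SAP Table 2; read literally, Table 12 would stop on the day of the second round. SAP 12.3 and Tables 13.1 to 13.6 make no provision for procedure relationship, which the protocol both specifies and collects, and do not identify AEs leading to treatment discontinuation.

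The effect is on the completeness of safety reporting only. No safety data are shown to be lost, and efficacy, power and error rates are unaffected. It still deserves correction because safety of administration is the primary objective and the remedy is cheap.

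Two assumptions remain. The first is that the AE form records drug and procedure attribution so that they can be separated; Protocol 5.2 and 5.2.1 indicate this, but the form is not in the documents. The second is that the discontinuation listing is possible, which depends on the CRF.

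**What to change.** **SAP 12.2.** Add Days 21, 30 and 60, and state that Table 12 is tabulated at all six time points in Protocol 4.2.13.

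**SAP 12.3 and Appendix A.**
1. State that Tables 13.3 and 13.6 use the study-drug attribution alone.
2. Add summaries of TEAEs and of serious TEAEs by closest relationship to the injection procedure, by arm, with the same Related/Not Related mapping.
3. Add a listing of TEAEs leading to a missed Day 14 injection or to discontinuation, with severity and both relationships, where the CRF captures the link.

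**Cost.** SAP wording, two tables and one listing. The tables use data already collected. The time-sensitive step is to check the CRF for the link from an AE to a missed dose and, if it is absent, to query sites before database lock.
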